5.1 Populations

The study population consists of all consecutive women attending regular screening mammography at Capio S:t Göran hospital in Stockholm (excluding, by necessity, any time period when the AI system is not functional). The data for each woman consists of: mammographic images, date of examination, age at examination, breast density measure, assessment by first radiologist, assessment by second radiologist, assessment by AI, assessment by consensus discussion (if any), pathology-verified cancer diagnosis (if any) including key cancer characteristics (listed above under 4.1 and 4.2).

5.2 Demographics and baseline data

All data will be presented using descriptive statistics. Continuous variables will be summarized using number of women, mean, standard deviation, median, interquartile range (IQR), minimum and maximum. Categorical variables will be categorized as described in the end-points and summarized using the number and percentage of cases in each category.

5.3 Setting the operating point of the AI system

A historical calibration dataset from the same institution will be used to set the AI operating point so that AI plus the recorded first reader would have a joint sensitivity 2 % higher than the joint sensitivity of the recorded first and second reader. The AI algorithm outputs a continuous score, and the threshold for the binary flagging decision was set to 0.534 (described in the WHO format research protocol). The threshold has so far not changed over the course of the study.

5.4 Primary analyses: Non-inferiority

Non-inferiority analyses in terms of sensitivity (rTPF as described on the prior page) of cancer as defined in the primary end-point (4.1) for initial read flagging performed by (i) AI and the first-reader radiologist compared to (ii) the first- and second-reader radiologists. The study has been powered for the primary analysis of cancer at the first screening examination (Figure 3), and adding cases at the subsequent follow-up time-points will further increase the statistical power.

5.5 Secondary analyses

In several of the secondary analyses we use the term **operating characteristics** referring to the various performance indicators used in evaluation of screening programs. These operating characteristics are based on the number of true and false, positive and negative, assessments by the various actors (radiologists and AI) at the various time-points (initial read, consensus discussion, tissue sampling) and based on the cancer ground truth defined by the primary end-points. Operating characteristics include sensitivity, specificity, recall rate, false negative rate, false positive rate, and the positive and negative predictive value at initial read (by each reader and by readers combined) and at consensus discussion (see Table 1). It should be noted that operating characteristics that relate to negative samples (such as the specificity, negative predictive values, and false negative rate) are not directly estimable under a screen-positive design (see Section 5.0). True and false negatives can however be estimated approximately with follow-up time, under the assumption that no new cancers develop and present clinically after the screen and that all cases are detected within the follow-up period. A longer follow-up period will increase the likelihood that cancers are discovered, but will also increase the chance of new cancers developing and being discovered. We will use a follow-up time of 23 months (the time of one screening cycle in a biennial screening program) for estimating statistics based on

estimates of true and false negatives (e.g. specificity, negative predictive values, and false negative rate). For each analysis of operating characteristics, we will perform a sensitivity analysis where women who were recalled due to symptoms (i.e., with radiologists finding no suspicious finding in the mammogram) are either excluded or re-classified as detected by all readers, AI and radiologists alike.

SENSITIVITY ANALYSES RELATED TO PRIMARY ANALYSIS

5.5.1 Repeat the primary analysis after re-classifying women who were recalled in screening due to symptoms (not due to mammographic signs) as detected by both AI and radiologists.

5.5.2 Repeat the primary analysis as a per-protocol-analysis where the examinations for which AI was not used are excluded.

5.5.3 Repeat the primary analysis without cancers with less aggressive characteristics: grade 1 in situ cancer grade 1, all in situ cancer.

5.5.4 Describe and compare the distribution of patient and cancer characteristics (described in 4.2.4) and stage (according to AJCC 7 and 8) between the two reader combinations in the primary analysis.

OTHER SECONDARY ANALYSES

5.5.5 Determine initial read operating characteristics (Table 1) for each combination of (i) initial read and (ii) arbitration as described in Figure 2.

5.5.6 Determine initial read operating characteristics for AI-only read below, and AI plus first-reader radiologist above, various AI score cut-off points.

5.5.7 Determine arbitration operating characteristics for an initial read by AI and one radiologist followed by either (i) the actual consensus discussion or (ii) arbitration decision based on recall of concordant cases and arbitration by second radiologist-decision for discordant cases.

5.5.8 Compare whether the cancer characteristics are different for the initial read cases flagged and not flagged between the AI reader and the radiologist readers.

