- Intervention Description: The AI CAD software has the product name Lunit INSIGHT MMG, which is CE certified. The version of the product that will be initially installed for this study is 1.1.6.1 (updated with future official releases). In the regular mammography screening process at the study hospital two radiologist readers review the image. During the study, AI CAD will be used as an independent third reader of screening mammograms and make a binary decision as do the other two readers (i.e., "flag" if anything suspicious is deemed present in the image, otherwise "healthy"). The AI CAD generates a continuous "score", for which a threshold value has been defined, above which the mammogram should be considered flagged, and below which it should be considered healthy. The threshold value was determined in a historic calibration dataset, in which the cut-off point resulted in a joint sensitivity of AI plus first reader radiologist which was 2% higher than the joint sensitivity of first reader and second reader radiologist. By this method the threshold value was preset to 0.534. The threshold value would not be changed during the course of the study.

Key Inclusion and Exclusion Criteria

All women attending screening mammography at Capio S:t Göran hospital will be considered for inclusion. The ethical review authority has waived the need to obtain individual written informed consent.

- Inclusion criterion: age 40-74 years, a standard four-view mammography examination was acquired (right MLO, right CC, left MLO, left CC)

- Exclusion criteria: having a breast implant (excluded by presence of either CCID or MLOID view position; ID = implant displaced) or having undergone mastectomy (excluded by not having a complete four-view mammography).

- For detailed information on planned statistical analysis – see separate Statistical Analysis Plan (SAP).

Study Type

Type of Study: Interventional study

Study design: All examinations will be reviewed by both human readers and AI CAD. During the course of the study, all mammograms that have been flagged by any of the three (human, human, AI) readers will go to a consensus discussion. The consensus discussion consists of an oral discussion of each flagged case, is held between at least two radiologists and results in a decision for each case to "recall" or to define as "healthy" (and not recall). During the course of this study, the radiologists in the

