This is a prospective clinical trial following a paired screen-positive design (9), with the aims to assess the performance of an AI algorithm combined with radiologists(s) compared to standard-of-care being two radiologists assessing screening mammograms in a true screening population (Figure 1). The study has paired design. All examinations will receive a flagging decision by: first reader, second reader, and AI. The first reader will not have access to AI. The second reader will first record her/his decision, then review AI to make a joint decision (forced to be flagged if the second reader and/or AI made a flagging decision). In the consensus discussion, two or more radiologists will discuss all flagged cases, having access to AI information. Since all decisions by individual readers will be recorded, it is possible to determine what the outcome would have been had one or two of the readers not been allowed to assess images, and to determine what the outcome would have been had the recall decision been performed by consensus decision (actual) compared to single reader arbitration of discordant cases (Figure 2).

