4.1 Primary endpoint

Diagnosed pathology-verified breast cancer; to be followed up at three time-points: (i) screen-detected - diagnosed after being recalled at the screening examination, (ii) adding non-screen-detected cancer diagnosed within 12 months after the screening examination and (iii) adding non-screen-detected cancer diagnosed within 23 months after the screening examination, not including the following screening examination (such that all cancers diagnosed over a full screening cycle are captured).

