$$\text{Positive predictive value} = \frac{TP}{TP+FP}$$

$$\text{Negative predictive value} = \frac{TN}{TN+FN}$$

Table 1. Definition of operating characteristics. Ground truth is defined by pathology-verified breast cancer for the three follow-up time points described in primary end-point (4.1). It should be noted that operating characteristics that relate to negative samples (such as the specificity, negative predictive values, and false negative rate) are not directly estimable under a screen-

positive design (see Section 5.0). True and false negatives can however be estimated approximately with follow-up time, under the assumption that no new cancers develop and present clinically after the screen and that all cases are detected within the follow-up period. A longer follow-up period will increase the likelihood that cancers are discovered, but will also increase the chance of new cancers developing and being discovered. We will use a follow-up time of 23 months (the time of one screening cycle in a biennial screening program) for estimating statistics based on estimates of true and false negatives (e.g. specificity, negative predictive values, and false negative rate).

Figure 1. The actual work flow in the study. If any one of the initial readers (First Radiologist, Second Radiologist or AI) decides to flag for a suspicious finding in the image, the exam is routed to the consensus discussion. The consensus discussion consists of an oral discussion between at least two radiologists (could be same or different as the initial readers) while reviewing the images of each case, and deciding to recall the woman for further diagnostics or to determine that she is healthy.

[figure not shown]

Figure 2. Alternative scenarios for which outcomes will be analyzed. The alternative at the top of each column is the actual implementation in the study. However, based on the recorded assessments of each radiologist and AI, other alternative scenarios will be analyzed in post-study analysis. To minimize the risk of incomplete cases, for any case of initial where AI is the only reader or combined with one radiologist, and the AI process fails, the AI assessment will be replaced by a radiologist read.

[figure not shown]
[figure not shown]

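### Analysis 5.5.7 cannot credit arbitration with cancers that consensus dismissed, so on screen-detected cancer its relative sensitivity is capped at 1

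*Combined protocol and SAP*

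**What the plan says.** SAP 5.5.7 asks for the operating characteristics of an initial read by AI and one radiologist, followed either by the consensus discussion as it took place or by an "arbitration decision based on recall of concordant cases and arbitration by second radiologist-decision for discordant cases". SAP Section 3 says that the recorded decisions make it possible to determine the outcome "had the recall decision been performed by consensus decision (actual) compared to single reader arbitration of discordant cases".

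Under the protocol (Study design, Figure 1), every flagged examination goes to consensus, and consensus alone decides who is recalled. The first time-point of the primary endpoint (SAP 4.1) is cancer that is "screen-detected - diagnosed after being recalled at the screening examination". The 12- and 23-month time-points add cancers diagnosed outside screening, "not including the following screening examination".

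The Table 1 legend says: "Ground truth is defined by pathology-verified breast cancer for the three follow-up time points". Section 5.5 and that legend assign statistics that rest on true and false negatives to 23 months. Section 5.5.7 names no time-point. The 2x2 layout in Section 5 marks only cells d and h as unknown.

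**The concern.** The two rules are judged against a truth that one of them produced. The screen-positive argument in Section 5 treats everyone who is positive on either side of a comparison as worked up. That fails here, because consensus stands between flagging and work-up. A woman recalled only by the hypothetical rule was in fact declared healthy and sent home, so for this contrast cells b and f are also unverified, and the SAP does not say so.

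The rules also differ in information. Consensus had the AI output. Reader 2's own decision was entered before the AI result was viewed (protocol, Blinding; SAP Section 3), so it was not made in knowledge of the disagreement that it is used to settle.

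At stake is how a descriptive comparison of two recall procedures after an AI read is interpreted. The primary analysis compares reader combinations at initial-read flagging and is not the subject of this point.

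**Working it through.** The SAP states no figure for 5.5.7, so there is none to reproduce. The 87% power in 5.7 belongs to the primary analysis and does not enter. Sensitivity below means TP/(TP+FN).

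**1. Screen-detected cancer.** Use the SAP's 2x2 table with arbitration as the novel rule and actual consensus as comparator. Among cancers flagged by AI or the one radiologist, *a* are recalled by both rules, *b* by arbitration only and *c* by consensus only. Relative sensitivity is (a+b)/(a+c). A cancer dismissed by consensus cannot be screen-detected, so b = 0 and the ratio is a/(a+c) ≤ 1, with a tie only if c = 0. If B cancers truly lie among the arbitration-only recalls, the ratio should be (a+B)/(a+c). The shortfall is B/(a+c), and all B fall in cell f.

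**2. At 23 months.** If s of the B present clinically before the next screen, the ratio is (a+s)/(a+c) and the shortfall is (B−s)/(a+c). New cancers arising in those women after the index screen would push the other way, so the net direction at 23 months is not fixed.

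**3. Illustration with counts (all assumed).** Consensus recalls 190 cancers, near the planning value 55,000 × 0.005 × 0.70 = 192.5 from 5.7. Arbitration misses c = 18 of them. B = 8, of which 3 surface by 23 months.

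| Truth used | Consensus | Arbitration | Gap (points) | Ratio |
|---|---|---|---|---|
| Screen-detected (s = 0) | 190/190 = 100% | 172/190 = 90.5% | 9.5 | 0.905 |
| 23 months (s = 3) | 190/193 = 98.4% | 175/193 = 90.7% | 7.8 | 0.921 |
| Complete (s = 8) | 190/198 = 96.0% | 180/198 = 90.9% | 5.1 | 0.947 |

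Arbitration is lower in every row. The sign would change only with B above 18.

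**4. How little the screen-detected ratio responds to the truth (all reader inputs assumed).** AI flags 80% of cancers and each radiologist 70%, independently. Consensus recalls a share k of flagged cancers. Arbitration then recalls 0.8×0.7 + (0.8×0.3 + 0.2×0.7)×0.7 = 0.826 of cancers, and consensus recalls 0.94k of them through AI or the first radiologist.

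- True ratio, 0.826/(0.94k): 0.925, 1.034 and 1.172 for k = 0.95, 0.85 and 0.75.
- Screen-detected ratio, 0.826k/(0.94k): 0.879 in all three cases.
- Ratio at 23 months if a share p of unrecalled cancers surfaces, 0.826[k+(1−k)p]/(0.94k), for p = 0.2 to 0.5: 0.888 to 0.902, 0.910 to 0.956, and 0.937 to 1.025.
- Cancers scored as arbitration false positives on screen-detected truth, with 55,000 × 0.005 = 275 cancers, 275×0.826×(1−k): about 11, 34 and 57.

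A simulation of 2,000 replicates per setting agreed. The screen-detected ratio averaged 0.88 each time and never exceeded 1.

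**5. False positives.** With 55,000 × 0.995 = 54,725 cancer-free women, 8 misclassified cancers add 8/54,725 = 0.015 percentage points to arbitration's false positive rate. Women recalled by consensus only and found free of cancer count against consensus, so arbitration's total can still be lower.

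**The case against.** Much of this is partly covered already. Section 5 says that absolute sensitivity and specificity cannot be estimated. The list of statistics moved to 23 months is introduced by e.g. and includes the false negative rate, so sensitivity in its ordinary sense arguably moves with it. The Preface leaves secondary endpoints and the 12- and 23-month results to later papers. Analysis 5.6.9 examines false negatives of the consensus, interval cancers included, by pattern of initial-read agreement. Analysis 5.5.7 has no hypothesis, margin or test. Section 5.5.7 also says openly that the second radiologist's decision is used, and Figure 2, which could not be seen here, may add qualifications.

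These arguments narrow the gap but do not close it. No time-point is tied to positive predictive value, rTPF or rFPF in 5.5.7. Section 5 allows screen-detected analyses from the first database release. Analysis 5.6.9 does not bound the 5.5.7 contrast, and nothing says that arbitration-only recalls are unverified.

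A reader might infer that consensus is favoured on false positives as well, whatever the truth, or that the trial would wrongly declare arbitration inferior. The documents support neither. The false-positive comparison can go either way, no formal conclusion is planned, the count illustration never changes sign, and the sign changes in step 4 need assumed consensus losses of 15% to 25% of flagged cancers.

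**Conclusion.** The point holds for relative sensitivity. On screen-detected cancer, arbitration can at best tie with consensus. This follows from the endpoint definition and the recall process and needs no assumed number. At 23 months the bias shrinks but is not removed, because cancers found at the next screen are not counted. The distortion of the false positive rate is small on any plausible count.

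The documents give no consensus loss rate and no share of dismissed cancers that surface. The size of the bias, its net direction at 23 months and whether it reverses the contrast therefore cannot be derived; the figures in steps 3 and 4 are illustrations only. This is a defect in one secondary analysis and in the Section 3 claim that rests on it.

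**What to change.** In SAP 5.5.7:

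1. State that every cancer-based measure for consensus versus arbitration (sensitivity, positive predictive value, rTPF, rFPF) uses the 23-month ground truth only, not screen-detected cancer.
2. Report examinations that arbitration would recall but consensus dismissed as a separate, unverified row, with the number diagnosed by 23 months (s). Give bounds for relative sensitivity, (a+s+u)/(a+c), over a stated range of undiagnosed cancers u in that row.

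In SAP Section 3, qualify the statement that the arbitration outcome can be determined. Say that arbitration-only recalls were not worked up, and that reader 2's decision was recorded before the AI result was seen.

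The cost is SAP wording and one extra tabulation from data already planned. The contrast is reported later and as a range instead of one figure. An analysis that also counts cancers found at the next screening round need not be required: it would credit arbitration with some cancers that developed after the index screen, and it goes beyond the planned 23-month follow-up.

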consensus discussion will have additional access to any information contained in the radiology system that has been generated by the AI CAD.

Date of First Enrollment

Study start was planned for March 2021. The first individual was included on April 1, 2021.

Sample Size

The study should enroll study persons with a total of 55,000 screening examinations.

Recruitment Status

Recruitment is on-going since April 1, 2021, and is expected to finish in May or June 2022.

Primary Outcome(s)

Diagnosed pathology-verified breast cancer; to be followed up at three time-points: (i) screen-detected - diagnosed after being recalled at the screening examination, (ii) adding non-screen-detected cancer diagnosed within 12 months after the screening examination and (iii) adding non-screen-detected cancer diagnosed within 23 months after the screening examination, not including the following screening examination (such that all cancers diagnosed over a full screening cycle are captured).

Secondary Outcome(s)

1. Reader flagging [YES|NO], i.e., each reader (radiologist or AI) makes an assessment that there is an abnormal finding warranting the examination to continue to the consensus discussion. Radiologist id codes will be recorded.
2. Consensus recall [YES|NO], i.e., a decision by the consensus discussion to recall the woman for further work-up. Radiologist id codes will be recorded.
3. Tissue sampling [YES|NO], i.e., decision by the radiologist to perform tissue sampling after additional diagnostic imaging of a recalled woman.
4. Process failures in generating the AI score or in transferring the AI score to the appropriate datapoint in the radiological RIS/PACS system.

In addition, several additional exploratory objectives and endpoints exist; see the detailed Statistical Analysis Plan.

Ethics Review

Approved on April 28, 2020, with registration id EPM 2020-00487 by the Ethical Review Authority of Sweden (email: [contact], [contact]).

Completion date

Estimated May to June, 2022.

Summary Results

N/A

IPD sharing statement

We plan to share individual participant-level data to the extent that the data can be considered anonymous by the responsible research body. A transfer agreement for academic research purposes will be required.

SPIRIT-AI additional items

Protocol Version

1.1, April 29, 2022.

Funding

See WHO above.

Roles and responsibilities

Protocol contributors

[name] PhD, Karolinska University Hospital: Principal Investigator

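### SAP 5.5.7(ii) has no arbitration read behind it: with the second reader's own flag it is two-of-three agreement, so its results for single-flag exams are set by rule and are not evidence on arbitration

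*Combined protocol and SAP*

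**What the plan says.** SAP 5.5.7 starts from an initial read by AI and one radiologist and sets the actual consensus discussion (i) against scenario (ii), "arbitration decision based on recall of concordant cases and arbitration by second radiologist-decision for discordant cases". The basis is given in SAP section 3: "Since all decisions by individual readers will be recorded, it is possible to determine what the outcome would have been" under other reader arrangements, including the actual consensus decision "compared to single reader arbitration of discordant cases". The Figure 2 legend gives the same source: "based on the recorded assessments of each radiologist and AI, other alternative scenarios will be analyzed in post-study analysis".

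The second reader leaves two records. SAP section 3 states: "The second reader will first record her/his decision, then review AI to make a joint decision". The joint decision is "forced to be flagged if the second reader and/or AI made a flagging decision". SAP 5.9 also treats the own and joint decisions as separate items, but 5.5.7 does not say which one arbitrates.

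The protocol's secondary outcomes define an initial flag: each reader "makes an assessment that there is an abnormal finding warranting the examination to continue to the consensus discussion". Recall is a separate, later decision taken at consensus.

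**The concern.** An arbitrator is a reader who is shown an exam on which two others disagree and who decides on recall. The trial has no such step. Any flag by any of the three readers sends the exam to a consensus of at least two radiologists. The second reader's own decision is entered before AI is shown, is not made to settle a disagreement between AI and the first reader, and is a flag for discussion, not a recall decision.

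Using that flag as the arbitration decision fixes the result for single-flag exams before any data are seen. A publication of (i) against (ii) could then report that single-reader arbitration loses the cancers AI adds, or that it removes false positives, although no arbitrator ever looked at those exams. Sensitivity, recall rate and predictive value in scenario (ii) would all carry this effect.

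**Working it through.** **Step 1: the rule.** Let AI, R1 and R2 be 1 if that reader flagged. Scenario (ii) recalls when AI = R1 = 1, and follows the arbiter when AI and R1 differ. The arbiter is either R2's own flag or the joint decision (1 if R2 or AI is 1).

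| AI | R1 | R2 | (ii), own flag | At least two of three | (ii), joint decision |
|---|---|---|---|---|---|
| 0 | 0 | 0 | 0 | 0 | 0 |
| 0 | 0 | 1 | 0 | 0 | 0 |
| 0 | 1 | 0 | 0 | 0 | 0 |
| 0 | 1 | 1 | 1 | 1 | 1 |
| 1 | 0 | 0 | 0 | 0 | 1 |
| 1 | 0 | 1 | 1 | 1 | 1 |
| 1 | 1 | 0 | 1 | 1 | 1 |
| 1 | 1 | 1 | 1 | 1 | 1 |

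The own-flag rule equals two-of-three agreement in all 8 patterns. The joint-decision rule equals AI or (R1 and R2). First-reader-only exams are recalled under neither. AI-only exams are never recalled under the first and always under the second.

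**Step 2: exception.** SAP 5.9 sets a missing second-reader decision to AI's when fewer than 1% of exams are affected. Such an exam with AI positive and the first reader negative would be recalled under the own-flag rule, with AI settling its own disagreement.

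**Step 3: direction at the first time-point.** SAP 4.1 defines a screen-detected cancer as one diagnosed after recall at screening. Leaving aside recalls for symptoms (SAP 5.5), every screen-detected cancer flagged by AI or R1 was therefore recalled by consensus and counts for (i). Every exam positive under the own-flag rule was flagged by AI or R1. So (ii) cannot exceed (i) on screen-detected cancers, and the shortfall is exactly the AI-only plus R1-only cancers. Once the 12- and 23-month cancers are added, this no longer holds. Consensus may have dismissed an exam that (ii) recalls automatically, and a later diagnosis would then count for (ii).

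**Step 4: size, as an illustration.** The plan gives no figure for 5.5.7. Inputs:
- Cancers: 55,000 × 0.005 = 275 (SAP 5.7).
- Sensitivities: AI 0.819 and first reader 0.774 (SAP section 2, retrospective cohort).
- Second-reader sensitivity Se2: not given, so assumed at 0.70 to 0.85.
- Reads assumed independent.

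AI-only = 275 × 0.819 × (1 − 0.774) × (1 − Se2) = 50.9 × (1 − Se2).

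R1-only = 275 × 0.774 × (1 − 0.819) × (1 − Se2) = 38.5 × (1 − Se2).

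| Assumed Se2 | AI-only | R1-only | Total |
|---|---|---|---|
| 0.85 | 7.6 | 5.8 | 13.4 |
| 0.774 | 11.5 | 8.7 | 20.2 |
| 0.70 | 15.3 | 11.6 | 26.8 |

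At Se2 = 0.774, the sensitivity of AI-or-R1 is 1 − 0.181 × 0.226 = 0.959. Subtracting 20.2/275 = 0.073 gives 0.886 under the own-flag rule. With the joint decision as arbiter, only the R1-only column is lost.

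Reads of the same image are unlikely to be independent. A simulation with correlated latent readings at Se2 = 0.774 gave totals of 23.4, 22.1 and 18.5 for correlations of 0.3, 0.6 and 0.8. Over Se2 from 0.70 to 0.85 and correlation from 0 to 0.8, the total ran from 11.1 to 30.2, or 4.7% to 11.8% of the cancers flagged by AI or R1.

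False positives with a single flag are excluded by the same rule. The documents give no rates from which to size that.

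**The case against.** The best defence is that 5.5.7 states its rule openly, is one secondary analysis and tests no hypothesis. In addition, 5.6.8 examines cancers on which readers disagreed, and 5.6.9 examines consensus errors by flag pattern, including flags by AI alone. All of that is true and limits the weight of the point. It does not remove it. Neither exploratory analysis tells the reader of 5.5.7 that (ii) is a majority vote, and section 3 still claims that the arbitration outcome can be determined.

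The illustration is also open to challenge. It counts cancers lost relative to the initial read, which equals the gap between (i) and (ii) only where consensus recalls every flagged cancer. It also mixes retrospective sensitivities based on 12-month follow-up with a plan that assumes a true positive fraction of 0.70. This stands, so the counts show order of magnitude only.

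A reader might infer more than the documents support:
- *Every single-flag cancer is lost whatever is done.* This depends on using the own flag, and the SAP does not exclude the joint decision.
- *The second reader is fully blind.* The protocol documents blinding to AI only, by instruction, and is silent on the first reader's result. The logic does not need it.
- *Scenario (ii) can never detect a cancer beyond standard of care.* Two of three flags do imply a flag by at least one radiologist, so this holds at flag level. At recall level it does not, because (ii) bypasses a consensus that can dismiss flagged exams.

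**Conclusion.** The concern holds as a matter of logic. On either reading of the second radiologist's decision, the difference between (i) and (ii) for single-flag exams is set by construction and is not evidence on how a single arbitrator would perform. Under the own-flag reading, (ii) is two-of-three agreement and cannot exceed (i) on screen-detected cancers, symptom recalls aside.

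The size is illustrative: about 13 to 27 of 275 cancers under independence, about 20 if the second reader matches the first. It depends on the assumed second-reader sensitivity and on reader correlation, so no single count should be quoted as the effect.

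It is tempting to treat (ii) as a lower bound on what arbitration would recall. It is not one: a real arbitrator could also dismiss a discordant exam that the second reader had flagged.

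The primary analysis concerns initial-read flagging. It and its sample size are unaffected. The matter is worth correcting because the remedy is cheap and changes what 5.5.7 can be said to show.

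**What to change.** - In 5.5.7(ii), state that the second reader's own decision, recorded before AI is shown, is the one used.
- In SAP section 3, in 5.5.7 and wherever Figure 2 shows the scenario (its content was not readable in the text at hand), label it *two-of-three agreement of initial flags (simulated, no arbitration read)*.
- Withdraw the statement in section 3 that the outcome under single-reader arbitration can be determined, and do not describe the scenario as a lower bound.
- Report the numbers of AI-only and first-reader-only cancers and false positives that the rule excludes.
- Add a reference row that recalls concordant positives and uses the actual consensus decision for exams on which AI and the first reader disagree. Label it as consensus, not as a single arbitrator. On the discordant exams it coincides with (i), so it isolates what the two-of-three rule does there.

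All of this uses data already recorded. The cost is SAP wording, the counts and one more row of output, together with a weaker claim about arbitration.
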